	
2) Duration of symptoms:
 
• A focal or global neurological deficit \geq 24 hours• A focal or global neurological deficit $<$ 24 hours if available neuroimaging indicates a new intracranial or subarachnoid hemorrhage (hemorrhagic stroke) or central nervous system infarction (ischemic stroke)• The neurological deficit results in death 
3) No other readily identifiable non-stroke cause for the clinical presentation (e.g. brain tumor, trauma, infection, hypoglycemia, peripheral lesion, pharmacological influences) to be determined by or in conjunction with designated neurologist.*
 
4) Confirmation of the diagnosis by at least one of the following:
 
• Neurologist or neurosurgical specialist, or• Neuroimaging procedure (CT scan or brain MRI)• Non-neurologist physician (if neurologist is not available)• Clinical presentation alone 
Stroke types will be classified as:
 
• Ischemic: an acute symptomatic episode of focal cerebral, spinal, or retinal dysfunction caused by an infarction of the central nervous system tissue• Hemorrhagic: an acute episode of focal or global cerebral or spinal dysfunction caused by intraparenchymal, intraventricular, or subarachnoid hemorrhage• Undetermined: if there is insufficient information to allow categorization as ischemic or hemorrhagic 
TIA Acute episode of a focal or global neurological deficit fulfilling the following criteria:
 
1) Resulting in at least one of the following:
 
• Change in level of consciousness• Hemiplegia• Hemiparesis• Numbness• Sensory loss affecting one side of the body• Dysphasia or aphasia• Hemianopia• Amaurosis fugax• Other neurological signs or symptoms consistent with stroke
--	--

	
2) Duration of deficit could be one of the following:
 
 • A focal or global neurological deficit < 24 hours • Any available neuroimaging does not demonstrate a new hemorrhage or infarct 
3) No other readily identifiable non-stroke cause for the clinical presentation (e.g. brain tumor, trauma, infection, hypoglycemia, peripheral lesion, pharmacological influences) to be determined by or in conjunction with designated neurologist.*
 
Notes: *Patients with non-focal global encephalopathy will not be reported as a stroke without unequivocal evidence based upon neuroimaging studies. #If a stroke is reported without evidence of confirmation of the diagnosis by one of these methods, the event may still be considered a stroke on the basis of the clinical presentation alone.

Tricuspid Regurgitation	Tricuspid Regurgitation (TR), tricuspid insufficiency or tricuspid incompetence describes a condition in which blood flow through the tricuspid valve flows in the incorrect direction during part of the cardiac cycle.
Unanticipated Adverse Device Effect (UADE) 21 CFR part 812.3 (s)	Serious adverse effect on health or safety or any life-threatening problem or death caused by, or associated with, a device, if that effect, problem, or death was not previously identified in nature, severity, or degree of incidence in the investigational plan or application (including a supplementary plan or application), or any other unanticipated serious problem associated with a device that relates to the rights, safety, or welfare of subjects.
Unanticipated Serious Adverse Device Effect (USADE)	Serious adverse device effect which by its nature, incidence, severity or outcome has not been identified in the current version of the risk analysis report NOTE Anticipated serious adverse device effect (ASADE) is an effect which by its nature, incidence, severity or outcome has been identified in the risk analysis report.

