7.8.3 Patient Enrollment

The enrollment overview is shown in Figure 1 in Section 1.2. A patient will be considered a "patient" and "provisionally enrolled" when they have signed the informed consent form. Provisionally enrolled patients will be reviewed by the Heart Team to assure that all inclusion criteria and none of the exclusion criteria are met at which point the patient will be considered "eligible". If a patient has signed the informed consent but are deemed not eligible, the patient is considered a "screen failure" and exit the study.

Eligible patients will be screened for imaging and anatomical suitability and if pre-procedural lab criteria are met. Once these criteria are met, the patient is considered "enrolled".

A Screening/Enrollment Log provided by the Sponsor, will be maintained at the study site. All patients assessed for study participation will be entered on the screening log. "Screen failures" will be recorded on the log with a failure reason.

The screening of patients qualifying for this study should be carried out in a sequential, prospective manner, such that all patients are offered the possibility of participating in the study and are therefore, evaluated according to the selection criteria defined in this protocol.

All patients that have signed the informed consent form, been assessed for study participation and deemed eligible for study participation by meeting the study criteria, will be assigned a

sequential patient ID number by the Study Sponsor. The patient ID number and initials (if applicable) shall be used to identify the patient on the site patient log in order to allow source verification with all study-related documents at the site.

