7.8.6 Imaging Assessments

Imaging assessments (TTE, TEE) shall be done according to the current version of the core lab echocardiographic acquisition protocol Appendix B. Severity of baseline MR shall be defined as described in Section 18.0 and confirmed by the echo core lab prior to enrollment.

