8 ADVERSE EVENTS, ADVERSE DEVICE EFFECTS AND DEVICE DEFICIENCIES

8.1 Reporting Procedure

Adverse events will be captured from the time of enrollment (after patient eligibility is confirmed, per section 7.8.3) until the study patient's participation has ended (i.e. completion of study or withdrawal of consent).

The Investigator will report all adverse events to the Sponsor as soon as possible, but no later than 10 working days after the Investigator first learns of the event (but no later than 3 calendar days after awareness for patients at EU sites)

Each adverse event must be reported on a separate AE CRF. In the event that the EDC system is not in service or is otherwise not accessible, the Sponsor must be notified by email

[REDACTED] The AE CRF should be completed as soon as possible thereafter.

At the time of initial notification, the following minimal information must be provided:

- Study site number
- Patient ID number
- Date of event
- Site's awareness date
- AE description
- Causal relationship to device and implant procedure, if known

The site will provide the Sponsor or designee copies of relevant supporting source documentation (e.g. admission H&P, implant procedure report, discharge summary, echocardiogram and laboratory results) for all adverse events requiring CEC adjudication (at a minimum, safety endpoints) and those events determined by the Sponsor to require additional investigation.

Study patients will be carefully monitored during the clinical study for any possible adverse event. All adverse events will be fully investigated by the Investigator. Appropriate treatment for the patient will be initiated while the study follow up continues. Adverse events must be followed

until resolution, the patient is lost to follow-up, the patient has withdrawn consent, or the adverse event is otherwise explained.

The Investigator will attempt to assess the involvement of the investigational device and / or study procedure in the adverse event. All observations and clinical findings, including the nature or the severity, will be documented on the appropriate case report form.

The Investigator will report all adverse events to their local Institutional Review Board/Ethical Committee and / or National Regulatory Agency in accordance with the applicable requirements.

8.1.1 Findings that do not require reporting to the sponsor:

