8.1.2 Pre-existing condition

[figure not shown]

Pre-existing medical conditions or symptoms reported prior to subject enrollment will not be recorded as an AE. In the event there is a worsening in the pre-existing medical condition or symptoms due to the device, implant procedure, or study related procedures, then an AE must be recorded.

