
Adverse Event (AE) (ISO 14155:2011)
	
Any untoward medical occurrence, unintended disease or injury, or untoward clinical signs (including abnormal laboratory findings) in patients, users or other persons, whether or not related to the investigational medical device NOTE 1- This definition includes events related to the investigational medical device or the comparator. NOTE 2- This definition includes events related to the procedures involved. NOTE 3- For users or other persons, this definition is restricted to events related to investigational medical devices.

Bleeding (M-VARC 2015)
	
I. Minor Any overt, actionable sign of hemorrhage (e.g., more bleeding than would be expected for a clinical circumstance, including bleeding found by imaging alone) that meets ≥ 1 of the following: requiring nonsurgical medical intervention by a health care professional; leading to hospitalization or increased level of care; prompting evaluation; or requires 1 or 2 U of whole blood or packed RBC transfusion and otherwise does not meet criteria for major, extensive, or life threatening bleeding.
 
II. Major Overt bleeding either associated with a drop in the hemoglobin of ≥ 3.0 g/dl or requiring transfusion of ≥ 3 U of whole blood or packed RBCs AND does not meet criteria of life-threatening or extensive bleeding.
 
III. Extensive Overt source of bleeding with drop in hemoglobin of ≥ 4 g/dl or whole blood or packed RBC transfusion ≥ 4 U within any 24-h period, or bleeding with drop in hemoglobin of ≥ 6 g/dl or whole blood or packed RBC transfusion ≥ 4 U (BARC type 3b) within 30 days of the procedure.
 
IV. Life-threatening Bleeding in a critical organ, such as intracranial, intraspinal, intraocular, or pericardial necessitating surgery or intervention, or intramuscular with compartment syndrome OR bleeding causing hypovolemic shock or hypotension (systolic blood pressure < 90 mm Hg lasting > 30 min and not responding to volume resuscitation) or requiring significant doses of vasopressors or surgery.
 
V. Fatal Bleeding adjudicated as being a proximate cause of death. Severe bleeding adjudicated as being a major contributing cause of a subsequent fatal complication, such as MI or cardiac arrest, is also considered fatal bleeding.

Cardiac Tamponade
	
Pressure on the heart that occurs when blood or fluid builds up

	in the space between the heart muscle (myocardium) and the outer covering sac of the heart (pericardium).

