	
 ○ Stroke ○ Sudden, unexpected death / unknown ○ Tamponade ○ Thromboembolism ○ Other CV cause 
If death was due to a heart failure, it will be sub-classified into:
 
 ○ LV dysfunction ○ RV dysfunction ○ Biventricular dysfunction 
Non-CV Death A diagnosis of non-CV death requires the primary cause to be clearly related to another condition due primarily to an identifiable non-CV cause or etiology. Specific diagnoses may include respiratory failure, pneumonia, trauma, suicide, or any other non-cardiovascular defined causes (e.g., liver disease, malignancies etc.) not included in the previous categories.
 
Primary cause of non-CV death The primary cause of non-CV death will be categorized using the following choices:
 
 ○ Adverse drug reaction or overdose ○ Cancer ○ Gastrointestinal ○ Liver failure ○ Non-cardiovascular infection and sepsis (e.g. pneumonia) ○ Pancreatic ○ Renal failure ○ Respiratory Failure ○ Trauma ○ Other non-CV cause

Degenerative/ Primary Mitral Regurgitation (M-VARC 2015)
	
Abnormal backflow of blood from left ventricle to left atrium due to underlying degenerative/structural mitral valve pathology. Severity is as defined by ASE.

Device success
	
Device is deployed as intended and the delivery system is successfully retrieved as intended at the time of the patient's exit from the cardiac catheterization laboratory. Per device analysis.

Conversion to open mitral valve surgery during a transcatheter
	
Sub-classified as:
 
 ○ Secondary to mitral valve apparatus damage or dysfunction, requiring surgical valve repair or replacement, or

procedure	
 ○ Secondary to procedural complications (such as cardiac perforation, removal of an embolized device, and so on)
Effective Regurgitant Orifice Area (ASE)	Cross-sectional area of the vena contracta of the regurgitant jet
Enrollment	Patient enrollment in this clinical study is established when a patient has signed the informed consent form agreeing to participate in the study and has been deemed eligible for study participation by meeting the study criteria.
Explant	Removal of the study device for any reason.

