	
Ordinary physical activity results in fatigue, palpitation, dyspnea, or anginal pain.
 
Class III: Patients with cardiac disease resulting in marked limitation of physical activity. They are comfortable at rest. Less than ordinary physical activity causes fatigue, palpitation dyspnea, or anginal pain.
 
Class IV: Patients with cardiac disease resulting in inability to carry on any physical activity without discomfort. Symptoms of cardiac insufficiency or of the anginal syndrome may be present even at rest. If any physical activity is undertaken, discomfort is increased.

Nonstructural Dysfunction	Abnormality extrinsic to the repair device that results in valve dysfunction (stenosis, regurgitation or both)
Patient	A person with the disease (mitral regurgitation) being screened to participate in the clinical study.
Pre-existing condition	A pre-existing condition is one that is present prior to enrollment in the trial
Procedural Success	Device success with evidence of MR reduction \leq MR2+ at discharge and without the need for a surgical or percutaneous intervention prior to hospital discharge. Per patient analysis.
Rehospitalization (M-VARC 2015 Definition and Sponsor)	
Rehospitalization
 
For the purpose of this trial, rehospitalization is defined as any unplanned admission to the hospital (including an emergency department visit) for either a diagnostic or therapeutic purpose following discharge from the index hospitalization. ER (Emergency Room) visits will be explicitly presented separately from the inpatient hospitalizations.
 
Rehospitalizations will be classified as either:
 
 ○ Admission to an inpatient unit (treated by a physician in a hospital for at least a 24 hour period) OR ○ Visit to an ER unit (typically less than 24 hours) AND diagnostic procedure and/or therapeutic intervention 
Additionally, duration of admission will be indicated as lasting:
 
 ○ < 24 hours OR ○ \geq 24 hours 
All rehospitalizations will be classified to determine whether the hospitalization was related to:

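### Adverse-event capture opens at enrollment, so new harm from a study-required screening procedure done after study consent but before enrollment, including in screen failures, falls outside AE reporting

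*Protocol*

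**What the plan says.** - **Protocol 7.8.3, Patient Enrollment.** A person becomes a provisionally enrolled patient "when they have signed the informed consent form". Heart Team review against the entry criteria makes the patient *eligible*. Then: "Eligible patients will be screened for imaging and anatomical suitability and if pre-procedural lab criteria are met". Only after that step is the patient *enrolled*. Screen failures go on a log with the reason.
- **Protocol 7.8.6, Imaging Assessments.** Study echocardiography follows the core-laboratory acquisition protocol, and the baseline regurgitation grade must be "confirmed by the echo core lab prior to enrollment".
- **Protocol 8.1, Reporting Procedure.** "Adverse events will be captured from the time of enrollment (after patient eligibility is confirmed, per section 7.8.3".
- **Protocol 17, Pre-existing condition.** "A pre-existing condition is one that is present prior to enrollment in the trial".
- **Protocol 8.1.2.** "Pre-existing medical conditions or symptoms reported prior to subject enrollment will not be recorded as an AE". The next sentence requires an AE when such a condition worsens because of the device, the implant procedure or study related procedures.
- **Protocol 17, Adverse Event, NOTE 2.** "This definition includes events related to the procedures involved".
- **Protocol 17, Enrollment.** The patient has consented and "has been deemed eligible for study participation by meeting the study criteria".

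**The concern.** Between study consent and enrollment a patient is already under the study's care but not yet inside its AE window. Tests done for the study in that interval can cause harm. Under the rules as written, a new injury in that interval is baseline history if the patient goes on to implant, and a line on the screening log if the patient does not.

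What is at stake is safety oversight, not an efficacy or safety estimate. The sponsor's safety review (8.2.8) and the DSMB's review of aggregate safety data (10.1.1) would have no AE record of such an event. Yet the AE definition and the worsening clause in 8.1.2 both show that the sponsor wants harm from study procedures recorded.

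**Working it through.** No sample size, power or event rate is involved, so the check is to put the rules in time order and run cases through them.

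**Order of steps.** Study consent (provisionally enrolled), then Heart Team review (eligible), then imaging, anatomical and laboratory screening (enrolled), then AE capture opens, then the procedure (Day 0).

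**Does screening really come before the window opens?** There are two possible readings of the trigger. Section 8.1 refers to eligibility being confirmed, whereas 7.8.3 makes eligible and enrolled separate steps. Section 7.8.7.11 also describes a patient who has been deemed eligible as still provisionally enrolled.
- If the trigger is *enrolled*, screening imaging comes first by the text of 7.8.3 and 7.8.6.
- If the trigger is *eligible*, the tests still come first, because the criteria depend on them. Exclusion 1 removes a patient whose screening TEE is unsuccessful, exclusion 2 concerns leaflet anatomy, and inclusion 10 requires a six-minute walk distance in functional regurgitation.

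The gap exists on both readings. The difference between them only adds doubt about when each site starts capture.

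**Cases, for a test done after study consent:**

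| Case | 8.1 window | Pre-existing rule (17, 8.1.2) | Recorded as AE? |
|---|---|---|---|
| New injury present before enrollment; patient proceeds | Not open | Pre-existing | No |
| New injury; patient then fails screening | Never opens | Never enrolled | No; log reason only |
| Existing condition worsened by a study procedure before enrollment | Not open | 8.1.2 says record it | Unclear; the two sections conflict |
| Harm that first appears after enrollment | Open | Not pre-existing | Yes |

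The first two rows are the gap and the third is a drafting conflict. The fourth shows that the gap is not total.

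**Effect on the endpoint.** SAP 5.1.1 sets the study start date at the procedure date, and the SAP 4 intent-to-treat population requires an incision. A pre-enrollment event would not enter the 30-day MAE analysis under either the present or the amended rule.

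**Size.** The stated maximum enrollment is 60 primary + 60 roll-in + 50 additional = 170 patients, with screen failures on top. This is a ceiling on enrollment, not a count of patients exposed to the gap. The documents give no screen-failure rate, no complication rate for screening tests, and no share of TEEs done after study consent.

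**The case against.** The strongest defence is that screening TEE is ordinary care. Section 7.8.1 exempts standard assessments from the consent-first rule, names TEE and TTE as examples, and allows them under a separate screening consent. The entry criteria set time windows before the intervention, not an order relative to consent. Many TEEs may therefore precede study consent, and the proposed change would not reach those. This stands, and it is the main reason to expect few events. It does not cover a TEE done for the study after study consent, or the six-minute walk test, which is not among the examples of standard assessments.

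Section 8.2.7 also treats complications of procedures as unrelated if the procedure would have been done without the investigational device. That governs how an event is classified once it is recorded. It does not justify leaving it unrecorded.

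A reader might infer more than the documents support:
- *That harm from screening TEE is never recorded.* Harm first appearing after enrollment is inside the window, and 8.1.2 at least calls for recording worsening due to study procedures.
- *That every consented patient, or all 170, is exposed.* Only those tested after study consent and before enrollment are, and that number is not given.
- *That section 6.1 already lists esophageal perforation as a risk of the screening TEE.* It lists it as a possible complication of the system and/or implant procedure, which itself includes a TEE.
- *That the AE definition and the capture rule contradict each other.* The definition says what an AE is, and 8.1 says when AEs are collected. A collection window may be narrower than a definition. The real misfit is between the worsening clause of 8.1.2 and the start point in 8.1.

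**Conclusion.** The point holds as a minor improvement to safety reporting. New harm from a study-required screening procedure, arising after study consent and before enrollment, has no route into the AE file, and for screen failures no AE record is described at all. The worsening clause in 8.1.2 does not close this, because it applies only to conditions that already existed and sits outside the window that 8.1 opens.

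The number of events cannot be computed from the documents. That it is small is a judgment resting on how often echocardiography precedes study consent. The primary safety endpoint does not change. The conclusion assumes that the enrollment overview (Figure 1) and AE classification (Figure 10), which could not be seen, do not set an earlier start for capture.

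**What to change.** - **7.8.3, 8.1 and Section 17 (Enrollment).** Use one definition of enrollment and one named trigger for AE capture.
- **8.1.** From study consent, capture all serious adverse events and any event related to a protocol-required procedure. Keep full AE capture from enrollment. Say whether a test done under the separate screening consent counts.
- **8.1.2 and Section 17 (Pre-existing condition).** Define pre-existing as present before study consent, so that the worsening clause and the capture window agree.
- **SAP 7.7.** List pre-procedure events separately, including those in screen failures, who belong to no analysis population. Exempt events known to precede the procedure from the partial-date rule in SAP 6.2. That rule would otherwise move an event dated only to the procedure month or year onto the procedure date, and so into the 30-day period.

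The cost is wording in four protocol places and two SAP sections, plus a few extra AE forms, mainly for screen failures. The 30-day MAE analysis stays as planned.
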